4.3 Exploratory Outcomes

Exploratory outcomes will include changes in characteristics related to opioid addiction including percentage of days using opioids and abstinence rates (Timeline Followback), motivation to quit (University of Rhode Island Change Assessment), craving for opioids (Visual Analog Scale), and related areas of psychiatric functioning.

- Timeline Follow-Back (TLFB; Sobell & Sobell, 1992): The TLFB obtains retrospective self-report of substance use by using a calendar and memory prompts to stimulate recall. Quantity and frequency assessments are made using this instrument (e.g., total amount of opioids used, percent of days using) as well as abstinence (yes/no). TLFB yields consistently high test-retest correlations and correlates well with other self-reports and collateral reports. The TLFB will assess consumption of opioids for 60 days prior to study entry, during the interventional phase and the follow-up phase. Use of nicotine and other drugs of abuse, including prescription drugs, will also be assessed using the TLFB.
- Urine Drug Screen (UDS) tests: Urine samples will be tested with a Multi-Drug Panel Test, which allows for the detection of THC/Marijuana, Cocaine, Phencyclidine, Opioids, Methamphetamines, Amphetamines, Barbiturates, and Benzodiazepines.
- Saliva Drug Screen tests: For follow-up visits conducted by telehealth, a Multi-Drug Panel saliva drug screen test may be optionally used in place of urine tests to facilitate ease of testing in a home setting.
- University of Rhode Island Change Assessment Scale (URICA; DiClemente & Hughes, 1999): This 32-item, self-reported questionnaire uses a five point Likert scale to assess levels of motivation to change according to the transtheoretical model (Precontemplation, Contemplation, Action, and Maintenance). This will be measured as the level of motivation to make changes may be mechanistically related to improving in opioid use.
- Visual Analog Craving Scale (VAS; McMillan & Gilmore-Thomas, 1996). At baseline, during the interventional visits, and at each follow-up visit, patients will be asked to report on the frequency, duration, and intensity of their opioid cravings on a 10 point (100 mm) VAS. This approach has been shown to yield a reliable and valid measure of craving in previous research.

- Generalized Anxiety Disorder Screener (GAD-7; Spitzer et al., 2006). The GAD-7 is a 7item self report instrument that will assess generalized anxiety symptomology.
- Five Facets of Mindfulness Questionnaire (FFMQ; Baers et al., 2006): The FFMQ assesses five components of mindfulness including observation, non-judgement of experience, non-reactivity to inner experience, acting with awareness, and description of experience.
- PTSD Checklist (PCL-5; Weathers et al., 2013): The PCL-5 is a 20-item self-report measure. The PCL-5 is similar in form to the PTSD Checklist (PCL) based on the DSM-5 (Weathers et al., 1993), which has excellent psychometric characteristics for screening and as a secondary indicator of PTSD symptom severity (McDonald & Calhoun, 2010).
- Insomnia Severity Index (ISI; Morin, 1993). The ISI is a 7-item, self-report measure that assesses perceived severity of insomnia. The items sum to produce a total score (range 0–28). The ISI has an internal consistency alpha coefficient of 0.74, and has shown convergent validity with other measures such as the Pittsburgh Sleep Quality Index and sleep diaries).
- Brief Pain Inventory (BPI; Cleeland, 1991). This 9-item questionnaire uses a 10-point Likert scale to assess the severity of pain and its interference on difference aspects of quality of life and function.

5.0 INCLUSION AND EXCLUSION CRITERIA/STUDY POPULATION

5.1 Initial Screening Methodology

Initial screening eligibility will be conducted by the PI or trained research personnel. Patients with a selfreported history of depression and opioid misuse or illicit opioid use for which they report being maintained on buprenorphine for at least thirty days will be eligible to complete informed consent and baseline evaluation.

5.2 Inclusion Criteria

A subject may be eligible for enrollment if all of the following inclusion criteria apply within the thirty days prior to randomization:

- 1. Between the ages of 18 to 65 years old.
- 2. Able to provide informed consent.
- 3. Meet DSM-5 criteria for Major Depressive Disorder, without psychotic features.
- 4. Score at least 20 on the Montgomery-Asberg Depression Rating Scale.
- 5. Fulfill a minimum of 4 of 11 current opioid use disorder criteria by DSM-5.
- 6. Have used opioids illicitly at least once in the past month.
- 7. Subjects must be on a standard of care pharmacotherapy for OUD (buprenorphine, methadone or naltrexone) for at least one month.
- 8. Subjects taking other psychotropic medications (e.g. anti-depressants or non-benzodiazepine anxiolytics) must be maintained on a stable dose for at least four weeks before study initiation.
- 9. Must consent to random assignment to ketamine or placebo control.

5.3 Exclusion Criteria

Patients will be excluded from the study if any of the following criteria apply:

- 1. They are considered an immediate suicide risk (by Columbia Suicide Severity Rating Scale of 4 or greater, a history of a suicide attempt in the past year, or by clinician judgment) or felt to be likely to require hospitalization during the course of the study.
- 2. They have a self-reported history of illicit ketamine use, or baseline urine drug testing positive for ketamine.
- 3. They are in acute opioid withdrawal (as evidenced by a score of 5 or above on the Clinician Opioid Withdrawal Scale). These subjects will be referred for clinical detoxification and pharmacotherapy induction. Subjects may be re-assessed for study eligibility after one month of treatment with a standard of care OUD pharmacotherapy.
- 4. Subjects who meet DSM-5 criteria for current bipolar disorder.
- 5. Subjects who meet DSM-5 criteria for current or history of psychotic spectrum disorders.

- 6. Women who are pregnant or nursing, and women who do not consent to use methods of highly effective birth control during the interventional phase of the study.
- 7. Subjects with current hypertension as defined by a systolic blood pressure (SBP) >140 mmHg or a diastolic blood pressure (DBP) >90 mmHg.
- 8. Subjects with a self-reported history of delirium for any cause.
- 9. A history of allergic or other adverse reaction to ketamine.
- 10. Clinically significant abnormal laboratory values, physical exam findings or self-reported medical conditions for which a transient increase in blood pressure could be significantly detrimental (e.g. glaucoma, brain aneurysms, cardiovascular disease, or end-stage renal disease).
- 11. Electrocardiogram (ECG) findings (obtained within thirty days prior to randomization) of tachycardia, prior myocardial infarction, myocardial ischemia, or aberrant conduction).

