1.3 Purpose and Objectives of the Study

The primary objective of the proposed study is to directly address this critical need by preliminarily testing the efficacy of ketamine in reducing opioid use and depression symptoms among individuals (N=30) with concurrent OUD and MDD who have failed to maintain abstinence despite treatment with a standard of care pharmacotherapy for OUD (i.e. buprenorphine, methadone or naltrexone). Effects on related symptoms and psychiatric conditions (e.g., cravings, motivation to quit, and anxiety symptoms) will also be explored. To accomplish this, we will use an intent-to-treat, double-blind, randomized clinical trial to compare the efficacy of ketamine to placebo control over a twice-weekly treatment schedule for four weeks. We will examine standardized, repeated dependent measures of clinical outcomes at baseline and multiple time points after the first treatment (48h to 8 weeks post initial treatment) with primary outcomes assessed at one month following the first treatment.

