3.0 INTERVENTION TO BE STUDIED

3.1 Overview of Study Medication

Ketamine was originally FDA approved in 1970 for pain control in conjunction with general anesthesia (Ketalar, 2018). The drug has since been evaluated in academic settings for the treatment of pain and a multitude of psychiatric indications. Ketamine has been increasingly studied in academic settings and used off-label in private practice settings over the past 10 years (Wilkinson et al., 2017). Ketamine undergoes extensive hepatic first pass metabolism, with an oral bioavailability of approximately 16% (Mathew et al., 2012). For induction of anesthesia, doses of 1 to 4.5 mg/kg IV or 6.5 to 13 mg/kg IM are recommended (Ketalar, 2018).

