3.3 Study Drug, Dose, Mode of Administration and Justification

Ketamine is concentrated at a dose of 50mg/ml and will be administered by intramuscular administration in the amount of 60 mg (1.2 ml). This dose follows the FDA-dosing guidelines of a maximum dose of 60 mg per treatment day, with a lifetime maximum of 8 treatments for psychiatric indications. Each study drug administration will be directly observed by the PI. For a 75 kg person, this dose will translate into an effective dose of 0.74 mg/kg based on an intramuscular bioavailability of 93%. While formal dose response studies for depression are lacking, ketamine has been most widely studied for psychiatric indications at 0.5 to 1.0 mg/kg given intravenously. Although there are only a few studies evaluating the use of ketamine in the treatment of substance use disorders, doses in these trials have ranged from 0.5 to 0.8 mg/kg given intravenously or 2 mg/kg given intramuscularly (Jones et al., 2018).

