8.0 RECRUITMENT METHODS

A chart review will be conducted for research purposes. Potentially eligible patients will be identified. The potentially eligible patients in the PIs practice will be informed about the study as the PI feels is appropriate. Then potential patients who have agreed to be contacted for future research by logging their MUSC Research Permissions preferences in MyChart will be contacted by phone and invited to participate. All other patients will be contacted through their providers to be informed of the study if the provider feels it is appropriate.

Recruitment will also be conducted through online (i.e. Craigslist) and flyer advertisements throughout the hospital and outpatient clinics at MUSC and other local clinics providing OUD treatment.

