10. STUDY DESIGN/METHODS

10.1 Study Overview

This is a double blind, placebo-controlled trial to assess the efficacy and safety of twice weekly intramuscular injections of ketamine in decreasing symptoms of OUD and MDD. Subjects will participate in a baseline visit to complete informed consent as well as complete assessments to evaluate study

eligibility and collect baseline data. Eligible participants will return within one week for the initial ketamine intervention procedure. Immediately prior to the interventional procedure, participants will be guided through a mindfulness-based exercise to facilitate relaxation and reduce anxiety during the intervention. Participants will be subsequently monitored for 120 minutes, during which time they will complete measures assessing their perception of the interventional experience. Participants initially assigned to the placebo group may choose to optionally complete 8 ketamine medication sessions beginning in Study WK #5.

	Groups A & B							
Visit #1: Baselir	ne Assessments		Study WK #0					
Visit #2: 1st Tx	Visit #3: 2nd Tx		Study WK #1					
Visit #4: 1st Tx	Visit #5: 2nd Tx		Study WK #2					
Visit #6: 1st Tx	Visit #7: 2nd Tx		Study WK #3					
Visit #8: 1st Tx	Visit #9: 2nd Tx		Study WK #4					
Visit #10: 1 WK follow-up	Visit #10: 1st KET Tx	Visit #11: 2nd KET Tx	Study WK #5					
Group A (Ketamine)		Placebo): Optional Visits						
Visit #11: 2 WK follow-up	Visit #12: 3rd KET Tx	Visit #13: 4th KET Tx	Study WK #6					
	Visit #14: 5th KET Tx	Visit #15: 6th KET Tx	Study WK #7					
Visit #12: 4 WK follow-up	Visit #16: 7th KET Tx	Visit #17: 8th KET Tx	Study WK #8					
	Visit #18: 1 WK follow-up		Study WK #9					
	Visit #19: 2 WK follow-up	2	Study WK #10					
		2 2	8					
			l					

Visit #20: 4 WK follow-up

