Columbia Suicide Severity Rating Scale	Assess for presence and severity of suicidal ideation	х											
Mini International Neuropsychiatric Interview	Assess for psychotic spectrum and bipolar disorder, presence and severity of OUD	х											
Pre-screening Questionnaire	To assess for basic eligibility criteria before completing a full baseline visit.	х											
Laboratory and Procedural Tests													
Pregnancy Test (female participants only)	Eligibility assessment		х	х	х	Х	Х	х	х	х			
Drug Screen	Eligibility assessment (benzos), secondary outcome measure		х	х	х	Х	Х	х	х	х	х	х	х
Serum blood tests (CBC, CMP)	Assessment of hemodynamic, hepatic, and renal function	X**											
Electrocardiogram (ECG)	Assessment of cardiac function	X**											

* Vital signs (blood pressure, pulse, and respiratory rate) will be obtained prior to treatment sessions, and at 45 and 90 minutes post-treatment. Pulse oximetry will be monitored immediately prior to treatment, and for 90 minutes after treatment. If there is an increase in systolic or diastolic blood pressure >30 mm Hg from baseline, or an increase in pulse rate >30 bpm from baseline, the measurements should be repeated after the patient has been in a resting position for 10 minutes. ** Will be performed for individuals with significant prior cardiac, renal or liver diseases.

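### The regimen is justified by a lifetime limit of 8 psychiatric ketamine treatments and uses all 8, but no eligibility criterion applies that limit to earlier, tolerated treatment

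*Combined protocol and SAP*

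**What the plan says.** Section 3.3 describes the 60 mg intramuscular dose as following FDA guidelines that cap the daily dose, "with a lifetime maximum of 8 treatments for psychiatric indications".

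The ketamine arm (Group A) is treated "over a twice-weekly treatment schedule for four weeks" (section 1.3). Placebo patients (Group B) "may choose to optionally complete 8 ketamine medication sessions beginning in Study WK #5" (section 10.1).

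Only two eligibility criteria deal with exposure to ketamine, both in section 5.3:

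- Exclusion 2: "They have a self-reported history of illicit ketamine use, or baseline urine drug testing positive for ketamine".
- Exclusion 9: "A history of allergic or other adverse reaction to ketamine".

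Inclusion 8 in section 5.2 asks that other psychotropic drugs be at a stable dose. It sets no limit on earlier ketamine. Section 3.1 acknowledges that ketamine is "used off-label in private practice settings over the past 10 years".

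**The concern.** A lifetime limit counts treatments given before the study as well as in it. When the study course equals the whole limit, the limit holds only for patients with no earlier psychiatric ketamine. The eligibility criteria are where that condition would have to be enforced, and they do not contain it. They deal with illicit use, ketamine in the urine at baseline, and bad reactions. Prescribed or trial ketamine that was tolerated and has since cleared is not mentioned.

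At stake is consistency with the limit that the protocol uses to defend its own dosing. If earlier treatment came to light after randomization, staff would have to let the patient pass the limit or cut the course short. Section 10.5 keeps the investigator blinded to the sequence, so during the blinded phase the investigator could not tell whose ketamine count is rising. The limit could then be applied only by unblinding or by cutting sessions without regard to arm.

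**Working it through.** **Inputs.** Limit: 8 psychiatric treatments (3.3). Schedule: 2 per week for 4 weeks (1.3). Optional course for Group B: 8 sessions (10.1, repeated in 12.1). Arms: 15 patients each (12.3). Criteria: 9 inclusions (5.2) and 11 exclusions (5.3).

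**Course length.** Group A: 2 × 4 = 8 ketamine treatments. Group B: 0 in the blinded phase + 8 optional = 8. Both equal the stated limit, so the margin is 8 − 8 = 0.

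**Effect of earlier treatment.** Let k be the number of earlier psychiatric ketamine treatments. A full course brings the lifetime total to 8 + k. The limit leaves 8 − k sessions and is passed once 9 − k study sessions have been given.

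| k | Total after a full course | Sessions left under the limit | Study session at which the limit is passed |
|---|---|---|---|
| 0 | 8 | 8 | never |
| 1 | 9 | 7 | 8th |
| 2 | 10 | 6 | 7th |
| 4 | 12 | 4 | 5th |

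A full course meets the limit only when k = 0.

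**Do the criteria ensure k = 0?** Of the 20 criteria, exclusion 2 removes illicit users and anyone with a positive baseline urine test. The urine test may catch very recent therapeutic use, but it cannot count lifetime treatments, and the drug panel described in 4.3 does not list ketamine. Exclusion 9 removes only patients who reacted badly. No other criterion bears on earlier ketamine. Sections 5.1, 10.4, 13.0 and 14.0, on screening, baseline assessment, monitoring and withdrawal, do not close the gap either.

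**How many patients.** A full ketamine course is offered to 15 patients (Group A only), and to up to 15 + 15 = 30 if every Group B patient takes the option. The documents give no share p with earlier psychiatric ketamine, so the values of p below are assumptions. The expected number runs from 15p to 30p:

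- p = 0%: 0
- p = 2%: 0.3 to 0.6
- p = 5%: 0.75 to 1.5

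These are patients offered a course with k of at least 1. Those who actually pass the limit are fewer, because with k = 1 all 8 sessions must be received.

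**The case against.** The strongest reply is that the limit is already written in 3.3 and staff have several chances to apply it. Section 8.0 says "A chart review will be conducted for research purposes". The pre-screening questionnaire in Table 2 exists "To assess for basic eligibility criteria before completing a full baseline visit". Section 10.4 includes a history and a medication review, section 11.0 allows medical records to be checked to clarify eligibility, and section 14.0 lets the investigator withdraw subjects. Section 5.2 is also permissive: meeting the criteria does not compel enrolment. On this view the gap is a drafting omission.

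Part of that stands. Earlier treatment could well be found, and staff could then act on 3.3. But none of these steps has a criterion that makes the finding disqualifying. The stated purpose of the medication review is harmful interactions, and the withdrawal provision does not mention a treatment count. Some candidates will also come through advertisements and may have no chart on site.

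A second reply is that the numbers are small and uncertain. This is correct. Section 12.2 expects 60% of enrolled patients to complete, and completion means only 75% of visits. Using 60% as a rough guide, 15 to 30 becomes 0.60 × 15 = 9 to 0.60 × 30 = 18, and the expected number becomes 0.18 to 0.36 at 2% and 0.45 to 0.9 at 5%. Even completers may miss a session, although with k of 2 or more fewer sessions are enough to pass the limit. The remark on off-label use in 3.1 is general and does not describe this population.

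Third, 3.3 cites no source for the limit and does not say how earlier treatments count, for example by route or when given as esketamine. That is also true. It is a reason to define the limit where it will be applied.

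**Conclusion.** The concern holds. The criteria in 5.2 and 5.3, applied as written, do not exclude a patient for whom the full course exceeds the limit on which 3.3 rests. The excess equals the number of earlier psychiatric treatments: a total of 9 after one, 10 after two, 12 after four.

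The conclusion takes the limit as the protocol states it and reads the word lifetime in its plain sense. It covers only earlier, tolerated ketamine given for a psychiatric indication; use in anesthesia or for pain is outside it. The number of patients affected is unknown and may be zero. The missing criterion is certain, but its practical effect is not: the documents show no specific harm from a ninth treatment, and outcomes, sample size and power are not involved. It is a modest point, worth correcting because the correction costs so little.

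**What to change.** Add to section 5.3 an exclusion for any earlier ketamine treatment for a psychiatric indication, and state whether esketamine counts. Because a full course meets the limit only with no earlier treatment, excluding any such treatment is the exact remedy. Ask about it on the existing pre-screening questionnaire and in the baseline medication evaluation.

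The cost is one line in the criteria and one question on an existing form. The downside is that a few candidates may become ineligible.

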6.0 NUMBER OF SUBJECTS

Approximately 30 patients are planned for enrollment in this study with no gender, race, or ethnicity exclusions.

7.0 SETTING

All procedures will be conducted in private research study rooms on MUSC campus.

8.0 RECRUITMENT METHODS

A chart review will be conducted for research purposes. Potentially eligible patients will be identified. The potentially eligible patients in the PIs practice will be informed about the study as the PI feels is appropriate. Then potential patients who have agreed to be contacted for future research by logging their MUSC Research Permissions preferences in MyChart will be contacted by phone and invited to participate. All other patients will be contacted through their providers to be informed of the study if the provider feels it is appropriate.

Recruitment will also be conducted through online (i.e. Craigslist) and flyer advertisements throughout the hospital and outpatient clinics at MUSC and other local clinics providing OUD treatment.

9.0 CONSENT PROCESS

9.1 Qualifications of Study Personnel Obtaining Informed Consent and Capacity of Participants

The research team have completed (or will complete upon hiring) the Miami Collaborative IRB Training Initiative (CITI) course and its associated tests in research ethics. Only the PIs, or Co-I's will obtain informed consent.

9.2 Location of Informed Consent

Informed consent will be obtained at the study research offices, in a private and interruption-free environment.

9.3 Method of Obtaining Consent

Study personnel will ensure that the participant is given full and adequate written and verbal information about the nature, purpose, possible risks and benefits of the study. There will be no mandatory waiting period prior to obtaining informed consent, however participants will not be required to make a decision at the time of initial contact. Participants will also be allowed to discuss the study with family or other individuals prior to giving their informed consent. After participants have reviewed the informed consent document, participants will be asked to relay their understanding of key elements related to the study procedures (i.e. voluntary nature of participation, basic study visit procedures, duration of study, anticipated risks and benefits) to ensure their understanding of the study prior to obtaining informed consent. Consent content will be reviewed as necessary to ensure that subjects have an adequate understanding to provide initial and ongoing consent. The participant's signed and dated informed consent will be obtained before conducting any study tests or procedures that are not related to their

Study WK #12

routine care. The Investigator will maintain the original, signed informed consent document. A copy of the signed informed consent document will be given to the participant.

